**5.4.2.3.2. Cytochrome P450 1A2 Inhibitors**

Anagrelide is metabolized at least in part by CYP1A2. Anagrelide is an inhibitor of cyclic AMP PDEIII. Thus, a dose reduction of approximately 50% for study treatment is appropriate for subjects who take potent CYP1A2 inhibitors systemically as concomitant medication (see [Appendix H](#)). This dose reduction should be accomplished by reducing doses of anagrelide or anagrelide-placebo from BID to QD.

NOTE: Once the course of therapy using a CYP1A2 inhibitor has been completed, the subject may resume his/her previous BID dose regimen of study treatment beginning the next day.

Investigators may refer to anagrelide label for further detailed information of potential interactions.

### **5.4.3. Dose Discontinuation of Ruxolitinib or Ruxolitinib Placebo/Anagrelide or Anagrelide Placebo**

#### **5.4.3.1. Discontinuation of Study Drugs for Hematologic Toxicity**

Study drug (ruxolitinib, anagrelide, or matching placebos) MUST be permanently discontinued if any 1 of the following Grade 3 or 4 hematologic toxicities (National Cancer Institute [NCI] CTCAE v 4.03) fails to resolve to  $\leq$  Grade 2 within 8 weeks of study drug interruption or if a lower restart dose or administration schedule subsequent to any of the following recurrent Grade 3 hematologic toxicities is either not available or likely to be clinically ineffective:

- Hgb < 8.0 g/dL (Grade 3).
- Platelet count <  $25 \times 10^9/L$  (Grade 4).
- ANC <  $0.5 \times 10^9/L$  (Grade 4).

#### **5.4.3.2. Discontinuation of Study Drug for Nonhematologic Toxicity**

Study drug (ruxolitinib, anagrelide, or matching placebos) MUST be permanently discontinued if any 1 of the following AEs fails to resolve to  $\leq$  Grade 2 within 8 weeks of study drug interruption or if a lower restart dose or administration schedule subsequent to any of the following nonhematologic toxicities is either not available or likely to be clinically ineffective:

- The occurrence of a Grade 4 laboratory or nonlaboratory abnormality attributable to study treatment (ruxolitinib, anagrelide, or matching placebo).
- The occurrence of a Grade 3 laboratory or nonlaboratory abnormality attributable to study treatments (ruxolitinib, anagrelide, or matching placebo) that remains at Grade 3 or worse for > 7 days duration and, for laboratory abnormalities, is deemed clinically significant in the judgment of the investigator.

#### **5.4.3.3. Dose Reduction Tapering Strategy (Optional)**

Following discontinuation of study drugs, symptoms from MPNs may return to pretreatment levels over a period of approximately 1 week.

When discontinuing or interrupting therapy for reasons other than thrombocytopenia or neutropenia, consider tapering the dose of study drugs gradually rather than discontinuing abruptly. A dose-tapering strategy may be considered, based on evaluation of the condition of the subject, current dosing regimen, and the clinical judgment of the investigator.

### **5.4.4. Dose Modifications for Subjects Receiving Open-Label Treatment**

The dose increase, decrease, and discontinuation rules described in Sections 5.4.1, 5.4.2, and 5.4.3 will be followed for subjects receiving open-label anagrelide or open-label ruxolitinib. Table 2 should be used to identify dose levels for the individual study medications.

## 5.5. Withdrawal of Subjects From Study Treatment

In the event that any subject permanently discontinues the study treatment, regardless of reason, reasonable efforts should be made to have the subject return to have the end-of-treatment (EOT) and follow-up evaluations completed as described in Section 6.6.

The date that the subject discontinued the study treatment and the specific reason for withdrawal will be recorded in the eCRF. This information will be used to summarize the reasons for study withdrawal.

### 5.5.1. Withdrawal Criteria

Subjects **must** be withdrawn from study treatment for the following reasons:

- Toxicities occur as noted in Section 5.4.3.
- Treatment is interrupted for  $\geq 8$  weeks, unless approved by medical monitor.
- Subject is unblinded before Week 52 for safety reasons.
- The subject becomes pregnant (positive urine pregnancy test, confirmed by positive serum pregnancy [serum human chorionic gonadotropin] test results).
- Consent is withdrawn.
- Further participation would be injurious to the subject's health or well-being, in the investigator's medical judgment.
- The study is terminated by the sponsor.
- The study is terminated by the local health authority, IRB, or IEC.

A subject **may** be discontinued from study treatment as follows:

- Subjects may choose to withdraw from the study at any time without penalty of jeopardizing their health care or loss of benefits to which the subject is otherwise entitled. Every reasonable effort should be made to determine the reason that a subject withdraws prematurely, and this information should be recorded in the eCRF.
- If, during the course of the study, a subject is found not to have met eligibility criteria, then the medical monitor, in collaboration with the investigator, will determine whether the subject should be withdrawn from the study (see Section 10.5, Protocol Adherence).
- A subject may be withdrawn from the study if, in the investigator's expert medical judgment, the subject is noncompliant with the study requirements. The sponsor should be consulted for instruction on handling the subject. Subjects may be withdrawn at the discretion of the FDA or the investigator.

### 5.5.2. Withdrawal Procedures

In the event that the decision is made to permanently discontinue the study treatment, the subject will be withdrawn from the study and the end-of-treatment visit should be conducted. Reasonable efforts should be made to have the subject return for a follow-up visit. These visits

are described in Section 6. The last date of the last dose of study treatment and the reason for subject withdrawal will be recorded in the eCRF.

**If a subject is withdrawn from the study treatments:**

- The study monitor or sponsor must be notified.
- The reason(s) for withdrawal must be documented in the subject's medical record and in the eCRF.
- The EOT visit should be performed, including diary completion.
- The date of the EOT visit should be recorded in the IXRS.
- In the event that a decision is made to permanently discontinue the study treatment and the subject is withdrawn from the study, reasonable efforts should be made to have the subjects return for a follow-up visit for safety until the time of the follow-up visit or until study treatment–related toxicities resolve, return to baseline, or are deemed irreversible, whichever is longest.

If the subject discontinues study treatment and actively withdraws consent for collection of follow-up data (safety follow-up or disease assessment), then no additional data collection should occur; however, subjects will have the option of withdrawing consent for study treatment but continuing in the follow-up period of the study for safety/efficacy assessments.

## **5.6. Concomitant Medications**

### **5.6.1. Permitted Medications**

All concomitant medications and treatments must be recorded in the eCRF. Any prior medication received up to 30 days before randomization will be recorded in the eCRF. Concomitant treatments or procedures that are required to manage a subject's medical condition during the study will also be recorded in the eCRF. [REDACTED]

Antibiotic prophylaxis for chronic treatment is permitted; subjects requiring acute antibiotic treatment at the time of screening must delay screening/enrollment until the course of antibiotic therapy is completed.

All randomized subjects should receive low dose aspirin (75 mg to 125 mg daily) unless medically contraindicated. In this case, other prophylactic antithrombotic agents may be used.

The subject needs to notify the investigational site about any new medications he/she takes after the start of the study drug. All medications (other than study drug) and significant nondrug therapies (including physical therapy and blood transfusions) administered after the subject starts treatment with study drug must be listed on the Concomitant Medications/Significant Nondrug Therapies After Start of Study Drug eCRF.

### 5.6.2. Restricted Medications

The following medications are restricted during the study:

1. Aspirin in doses exceeding 125 mg per day is not permitted. Low-dose aspirin is permitted. Acetaminophen and nonsteroidal anti-inflammatory agents (eg, ibuprofen, NSAIDs) may be used at over-the-counter doses. Subjects receiving over-the-counter NSAIDs should not exceed the recommended dose and should be encouraged to use gastroprotective agents (antacids, H2 antagonists, or proton pump inhibitors).
2. Inducers of CYP3A4 ([Appendix H](#)) may be used with caution, and investigators should seek other options if available.
3. Moderate CYP3A4 inhibitors ([Appendix H](#)) may be used with caution. Differences in individual sensitivity and variation in potency of inhibition of various CYP enzymes may result in the need for a reduced dose of ruxolitinib during a period of concomitant medication use. If required for safety, the study drug dose may be reduced from BID to QD in these circumstances. The sponsor's medical monitor may be consulted for advice when using these agents.
4. Use of potent inhibitors of CYP3A4 and CYP1A2 should be avoided where possible. See Section 5.4.2.3 for required dose reductions and [Appendix H](#) for included CYP inhibitors.
5. If concomitant administration of an anticoagulant/antiplatelet medication is indicated, then caution and enhanced monitoring is required. History of thrombocytopenia and any concurrent ruxolitinib-related thrombocytopenia should be a factor in the choice of anticoagulant and dose.

### 5.6.3. Prohibited Medications

The following medications are prohibited during the study:

1. Any prior or concomitant use of another JAK inhibitor.
2. Concurrent use of anagrelide or HU.
  - a. Prior anagrelide use is allowed provided the reason for discontinuation is not AE-related and anagrelide is stopped at least 28 days before the start of study medications (ie, Day 1).
  - b. Treatment with HU can be stopped at any time once one of the inclusion criteria for HU refractoriness or resistance have been met, and up to the day before the first dose of study treatment (ie, Day 1).
3. Any investigational medication (other than ruxolitinib) that is not approved for any indication.
  - a. Use of such medications within 30 days or 5 half-lives, whichever is longer, before the first dose of study drug and during the study through the safety follow-up visit is prohibited.

4. Steroid doses greater than the equivalent of 10 mg prednisone per day. During study participation, if a subject requires steroids for a comorbid condition, then continuation in the study will be considered on an individual basis by the sponsor and the investigator (unless part of study treatment dose-tapering strategy).
5. Use of busulfan, interferon alpha, pegylated interferon, or any investigational medication used to treat ET is not permitted at any time beginning on Day -30 up until the time that ruxolitinib therapy is permanently discontinued. Use of androgens to treat anemia is permitted.

7. Erythropoietin is not allowed during the study.
8. Romiplostim or eltrombopag are not permitted beginning with the baseline visit (Day -7) through the final dose of ruxolitinib.
9. St John's Wort and rifampin are not permitted at any time during participation in the study.
10. Any medications that may prolong QTc interval of the ECG.

See [Appendix H](#) for a list of CYP inhibitors and inducers.

See [Appendix J](#) for a list of drugs that may cause prolongation of QT interval.

## 6. STUDY ASSESSMENTS

All study assessments will be performed as indicated in the schedule of assessments ([Table 3](#)), and all laboratory assessments will be performed as indicated in [Table 4](#). The schedule of assessments and laboratory assessments for subjects in Group B (anagrelide) who cross over to open-label ruxolitinib after Week 52 are provided in [Table 5](#) and [Table 6](#). [Table 7](#) presents a summary of clinical laboratory analytes to be assessed. The order of assessments is suggested by the order of mention within the schedule. See [Section 7](#) for instructions on each assessment. Further details of study procedures and assessments can be found in the study reference manual.

**Table 3: Schedule of Assessments**

	Section	Screening Days -35 to -8	Baseline Days -7 to -1	Blinded Treatment (All Subjects)						Open-Label Treatment		EOT	Safety Follow-Up 30-37d After Last Dose	Notes	
				W1-W3			W4-W52 q4w	W34-W50 q4w (lab only)	Subjects Who Do Not Cross Over	Subjects Who Cross Over					
				D1	D8 (±2d)	D15 (±2d)	D22 (± 2d)	D7 (± 3d)	D7 (± 3d)	W56 + q12w	W56+ q12w				
Informed consent	7.1	X									See Table 5				
Contact IXRS	7.2	X		X				X		X					
Review inclusion and exclusion criteria	7.5.1	X		X											
Demography, medical history	7.3	X													
Prior/concomitant medications	7.4	X	X	X	X	X	X	X		X			X	X	
Vital signs	7.5.4	X	X	X	X	X	X	X		X			X	X	Vital signs collected after 5 min rest in recumbent, semirecumbent, or sitting position.
Physical examination, body weight, height	7.5.3	X*		X	X	X	X	X		X			X*	X	* Comprehensive examination at screening and EOT visits, targeted physical examination at all other indicated visits. Height at screening only.
ECOG status	7.7.1	X*		X*				X		X			X		* Performance status must be 0, 1, or 2 at baseline.
/liver palpation	7.6.3	X	X					X		X			X	X	Using flexible ruler provided for study.
Complete MPN-SAF questionnaire	7.7.4		X					X*					X*		*Weeks 32 and 52 and/or EOT visits.
Overall response assessment	7.6.2							X*				X*		* Weeks 32 and 52 and/or EOT visits.	
12-lead ECG	7.5.5	X						X*				X		* Week 52.	

**Table 3: Schedule of Assessments (Continued)**

	Section	Screening Days -35 to -8	Baseline Days -7 to -1	Blinded Treatment (All Subjects)							Open-Label Treatment		EOT	Safety Follow-Up 30-37d After Last Dose	Notes
				W1-W3			W4-W52 q4w	W34-W50 q4w (lab only)	W56 + q12w	W56+ q12w	Subjects Who Do Not Cross Over	Subjects Who Cross Over			
				D1	D8 (±2d)	D15 (±2d)	D22 (± 2d)	D7 (± 3d)	D7 (± 3d)	D7 (± 7d)	D7 (± 7d)	D7 (± 7d)			
Laboratory tests	7.5.6	X	X	X	X	X	X	X*	X*	X	See Table 5	X	X	* Weeks 32-52 are evaluation period for primary endpoint. Should ALL be carefully monitored by sites.	
Review AEs	7.5.2	X	X	X	X	X	X	X		X		X	X		
Transfusion history/status	7.4	X	X	X				X		X		X	X		
Drug dispensed	7.10.2			X				X		X					
Drug accountability	7.10.3							X		X		X			

MPN-SAF = Myeloproliferative Neoplasm–Symptom Assessment Form (paper/pencil format).

**Table 4: Schedule of Laboratory Assessments**

[figure not shown]
	Section	Screening Days -35 to -8	Baseline Days -7 to -1	Blinded Treatment (All Subjects)						Open-Label Treatment		EOT	Safety Follow-Up 30-37d After Last Dose	Notes
										Subjects Who Do Not Cross Over	Subjects Who Cross Over			
				W1-W3			W4- W52 q4w	W34-W50 q4w (lab only)		W56+ q12w	W56+ q12w			
				D1	D8 (±2d)	D15 (± 2d)	D22 (± 2d)	D7 (± 3d)	D7 (± 3d)	D7 (± 7d)	D7 (± 7d)			
Local laboratory assessments											See Table 6			
Hematology	7.5.6	X	X*	X*	X	X	X	X**	X**	X		X	X	* Should be taken as close as possible to Day 1 but may be drawn up to 3 days before first dose. Only 1 sample for baseline/Day 1 is required. ** Weeks 32-52 are evaluation period for primary endpoint: Should ALL be carefully monitored by sites.
Ferritin level	7.5.6		X											
Coagulation panel	7.5.6	X	X*	X*								X		* Should be taken as close as possible to Day 1 but may be drawn up to 3 days before first dose. Only 1 sample for baseline/Day 1 is required.
Serum chemistries	7.5.6	X	X*	X*	X	X	X	X		X		X	X	* Should be taken as close as possible to Day 1 but may be drawn up to 3 days before first dose. Only 1 sample for baseline/Day 1 is required.
Urine pregnancy test	7.5.6.1			X				X		X				Females of childbearing potential. Test should be repeated if required by local regulations. Not needed if FSH elevated or amenorrheic > 1 year.

**Table 4: Schedule of Laboratory Assessments (Continued)**

	Section	Screening Days -35 to -8	Baseline Days -7 to -1	Blinded Treatment (All Subjects)						Open-Label Treatment		EOT	Safety Follow-Up 30-37d After Last Dose	Notes
										Subjects Who Do Not Cross Over	Subjects Who Cross Over			
				W1-W3				W4- W52 q4w	W34-W50 q4w (lab only)	W56+ q12w	W56+ q12w			
				D1	D8 (±2d)	D15 (± 2d)	D22 (± 2d)	D7 (± 3d)	D7 (± 3d)	D7 (± 7d)	D7 (± 7d)			
Bone marrow biopsy and analysis	7.6.4	X*						X**		X***	See Table 6	X		Local laboratory evaluation and pathology report. * Predose biopsy not required if previous biopsy and report from 2 months before screening are available. ** Weeks 32 and 52 only. *** Optional at Week 104 and 152 for ruxolitinib-treated subjects only.
Central laboratory samples														The central laboratory is the sponsor or designee.
Bone marrow biopsy and analysis	7.6.4	X*						X**		X***		X		Samples sent for banking to central laboratory. See notes for local laboratory collections above.
Lipid panel	7.5.6	X		X*	X	X	X	X		X		X	X	* Should be taken as close as possible to Day 1 but may be drawn up to 3 days before first dose. Only 1 sample for baseline/Day 1 is required.
Serology hepatitis A, B, and C	7.5.6	X												
Urinalysis	7.5.6	X		X		X		X		X		X	X	

**Table 4: Schedule of Laboratory Assessments (Continued)**

	Section	Screening Days -35 to -8	Baseline Days -7 to -1	Blinded Treatment (All Subjects)						Open-Label Treatment		EOT	Safety Follow-Up 30-37d After Last Dose	Notes
										Subjects Who Do Not Cross Over	Subjects Who Cross Over			
				W1-W3			W4- W52 q4w	W34-W50 q4w (lab only)	W56+ q12w	W56+ q12w				
D1	D8 (±2d)	D15 (± 2d)	D22 (± 2d)	D7 (± 3d)	D7 (± 3d)	D7 (± 7d)	D7 (± 7d)							
Serum pregnancy	7.5.6.1	X									See Table 6	X		Not needed if FSH elevated or amenorrheic > 1 year. Test should be repeated if required by local regulations.
FSH	7.5.6.1	X												To document hormonal menopause.

FSH = follicle-stimulating hormone

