#### 3.1. Subject Inclusion Criteria

A subject who meets all of the following criteria may be included in the study:

1. Men and women, aged 18 or older.
2. Subjects diagnosed with ET according to revised WHO 2016 criteria ([Appendix A](#); [Arber et al 2016](#)).
3. Subjects who are resistant to or intolerant of HU ([Appendix B](#)), that is, fulfilling at least 1 of the following criteria:
  - a. Platelet count  $> 600 \times 10^9/L$  after 3 months of at least 2 g/day of HU (2.5 g/day in subjects with a body weight over 80 kg) OR at the subject's maximally tolerated dose if that dose is  $< 2$  g/day.
  - b. Platelet count  $> 400 \times 10^9/L$  and WBC count  $< 2.5 \times 10^9/L$  or hemoglobin (Hgb)  $< 10$  g/dl at any dose of HU.
  - c. Presence of leg ulcers or other unacceptable muco-cutaneous manifestations at any dose of HU.
  - d. HU-related fever.
4. Platelet count  $\geq 650 \times 10^9/L$  at screening.
5. WBC  $\geq 11.0 \times 10^9/L$  at screening.
6. ECOG performance status 0 to 2.
7. Known status of JAKV617F mutation.

8. Willingness to avoid pregnancy or fathering children based on the following criteria ([Appendix G](#)):
  - a. Woman of nonchildbearing potential (ie, surgically sterile with a hysterectomy and/or bilateral oophorectomy OR  $\geq 12$  months of amenorrhea and at least 50 years of age).
  - b. Woman of childbearing potential who has a negative serum pregnancy test at screening and negative urinary test before the first dose on Day 1 and who agrees to take appropriate precautions to avoid pregnancy (with at least 99% certainty) from screening through safety follow-up. Permitted methods that are at least 99% effective in preventing pregnancy should be communicated to the subject and their understanding confirmed.
  - c. Man who agrees to take appropriate precautions to avoid fathering children (with at least 99% certainty) from screening through safety follow-up. Permitted methods that are at least 99% effective in preventing pregnancy should be communicated to the subject and their understanding confirmed.

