**Table 7: Laboratory Tests: Required Analytes**

Serum Chemistry	Hematology	Urinalysis With Microscopic Examination	Hepatitis Screening	Coagulation
Albumin Alkaline phosphatase ALT AST Bicarbonate Blood urea nitrogen Calcium Chloride Creatinine Ferritin Glucose Lactate dehydrogenase Phosphate Potassium Sodium Total bilirubin Direct bilirubin (if total bilirubin is elevated above ULN) Total protein Uric acid	Complete blood count, including reporting of % blasts: Hemoglobin Hematocrit Platelet count Red blood cell count WBC count	Color and appearance pH and specific gravity Bilirubin Glucose Ketones Leukocytes Nitrite Occult blood Protein Urobilinogen	Hepatitis B surface antigen Hepatitis B surface antigen antibody Hepatitis A, B core antibody HBV-DNA HCV antibody HCV-RNA	PT aPTT INR
	Differential count, including:	Lipid Panel		Pregnancy Testing
	Basophils Eosinophils Lymphocytes Monocytes Neutrophils  Absolute values must be provided for: WBC differential laboratory results: Lymphocytes Neutrophils	Total cholesterol Triglycerides Low density lipoprotein High density lipoprotein		Female subjects of childbearing potential only require a serum test at screening and EOT and a urine pregnancy test at each study visit when the test is requested. Pregnancy tests (serum or urine) should be repeated if required by local regulations. FSH

Note: Additional tests may be required, as agreed by investigator and sponsor, based on emerging safety data.

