##### **7.5.6.1. Pregnancy Testing**

A serum pregnancy test will be required for all women of childbearing potential at screening and at the EOT visit. An FSH test will be performed on females who have been amenorrheic for > 1 year. If FSH levels are elevated to postmenopausal range, no pregnancy testing is required for these female subjects. Urine pregnancy tests will be conducted as outlined in [Table 4](#) and [Table 6](#), as medically indicated, or per country-specific requirement. Urine pregnancy tests will be performed locally.

If a urine pregnancy test is positive, then the results should be confirmed with a serum pregnancy test. If the serum pregnancy test is negative after a urine test was positive, then the investigator will assess the potential benefit/risk to the subject and determine whether it is in the subject's best interest to resume study treatment and continue participation in the study.

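### Table 4 waives pregnancy tests on amenorrhea alone, contrary to criterion 8 and Section 7.5.6.1; separately, Table 6 ties the crossover-eligibility urine test to local regulations

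*Protocol*

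**What the plan says.** Five places in the Protocol set the pregnancy-testing rule.

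- **Table 4**, in the notes to both the urine row and the serum row: "Not needed if FSH elevated or amenorrheic > 1 year". The urine row is addressed to women of childbearing potential. Neither note has an age condition.
- **Section 3.1, criterion 8.** Under 8a, a woman who is not surgically sterile is nonchildbearing only with at least 12 "months of amenorrhea and at least 50 years of age". Under 8b, a woman of childbearing potential needs a "negative serum pregnancy test at screening and negative urinary test before the first dose on Day 1".
- **Section 7.5.6.1**: "A serum pregnancy test will be required for all women of childbearing potential at screening and at the EOT visit". It continues: "An FSH test will be performed on females who have been amenorrheic for > 1 year", and then: "If FSH levels are elevated to postmenopausal range, no pregnancy testing is required for these female subjects". For urine tests it refers back to the schedules: "Urine pregnancy tests will be conducted as outlined in" Tables 4 and 6, with further tests when medically indicated.
- **Table 7**: women of childbearing potential "require a serum test at screening and EOT and a urine pregnancy test at each study visit when the test is requested". It states no waiver for amenorrhea or FSH.
- **Table 6**, for Group B subjects who cross over: a urine test is marked at the crossover eligibility visit, but the note limits it to women of childbearing potential where local regulations require it. There is no serum row.

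Three other provisions bear on crossover. Section 4.4 re-applies the exclusion criteria, exclusion 15 is pregnancy or breastfeeding, and Table 5 allows open-label ruxolitinib to be dispensed at the eligibility visit.

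**The concern.** The *or* in Table 4 turns what Section 7.5.6.1 treats as a reason to measure FSH into a reason to stop testing. A woman can therefore be of childbearing potential under criterion 8 and still be exempt from every scheduled pregnancy test in Table 4. A site gets a different instruction depending on which page it follows.

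The safeguards that come later depend on a test being done. Section 5.5.1 requires withdrawal on a positive urine test confirmed by serum, and Section 8.5 requires immediate discontinuation once pregnancy is confirmed. Section 1.2.1 reports no teratogenicity in rat or rabbit, but increased postimplantation loss at higher doses.

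The crossover visit raises a similar question by another route. It can mark a Group B woman's first exposure to ruxolitinib, yet on a literal reading the only test marked there may be skipped. Day 1 has a firmer check, through criterion 8b.

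**Working it through.** No sample size, power or alpha figure is involved. The check compares the rules for each type of woman, then counts tests and intervals.

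**Step 1. Which women are treated differently?** All are assumed not surgically sterile.

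| Woman | Table 4 | Section 7.5.6.1 | Criterion 8a |
|---|---|---|---|
| Age 50 or over, amenorrhea over 1 year | waived | waived if FSH postmenopausal | nonchildbearing |
| Under 50, amenorrhea over 1 year, FSH postmenopausal | waived | waived | childbearing potential |
| Under 50, amenorrhea over 1 year, FSH not postmenopausal | **waived** | **not waived** | **childbearing potential** |
| Under 50, not amenorrheic, FSH elevated | waived | FSH not ordered | childbearing potential |

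The third row is the practical case. The second is a wording mismatch with 8a that carries little clinical risk. The fourth is nearly empty, because Section 7.5.6.1 orders FSH only after more than 1 year of amenorrhea.

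**Step 2. How many tests does Table 4 drop for the woman in the third row?**

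- Screening serum: 1
- Day 1 urine: 1
- Four-weekly urine, Weeks 4, 8, …, 52: 52 / 4 = 13
- EOT serum: 1
- Total: 1 + 1 + 13 + 1 = 16, before the 12-weekly urine tests from Week 56

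**Step 3. Which of the 16 are required elsewhere without condition?**

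- Screening serum: criterion 8b, Section 7.5.6.1, Table 7
- Day 1 urine: criterion 8b
- EOT serum: Section 7.5.6.1, Table 7

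That is 3. The remaining 16 − 3 = 13 are the four-weekly urine tests. Criterion 8b does not reach past Day 1, Table 7 covers these tests only when requested, and Section 7.5.6.1 takes their schedule from Table 4. What stands against Table 4 here is the narrower FSH-based waiver in Section 7.5.6.1.

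**Step 4. How old is the last scheduled urine test at crossover?**

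- Week 52 to Week 56: (56 − 52) × 7 = 28 days.
- With visit windows of ±3 days (Week 52) and ±7 days (Week 56): 28 − 10 = 18 to 28 + 10 = 38 days.
- Section 6.3.1 allows a delay of up to 4 weeks to meet eligibility. If that is the same four weeks as Week 52 to Week 56, nothing changes. If it comes on top, the upper end is 38 + 28 = 66 days. The text does not settle which.
- A later crossover from open-label anagrelide: up to about 12 × 7 = 84 days, and less if it falls soon after a 12-weekly visit.

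**The case against.** The strongest reply is that Table 4 is shorthand for Section 7.5.6.1. Both pregnancy rows cite that section, Section 6 sends sites to Section 7 for instructions on each assessment, and the FSH row next to the serum row says its purpose is to document menopause. A site that follows the reference finds the narrower waiver. This reduces the risk but does not remove it. Section 6 also tells sites to perform laboratory assessments as Table 4 shows, it does not say which text prevails, and for urine tests Section 7.5.6.1 points back to Table 4.

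A reader might infer that all 16 tests are contradicted. Only 3 are; for the other 13 the conflict is indirect. Nor does it follow that women of childbearing potential enter untested, because criterion 8b requires two negative tests regardless of Table 4. Contraception is also mandatory.

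On Table 6, the local-regulations phrase appears twice in one note. The matching Table 4 note attaches it only to repeat testing, so a drafting slip is likely. Table 5 also sends sites to Table 7, requires review of the inclusion and exclusion criteria at the eligibility visit, and Section 6.3.1 provides for an unscheduled safety visit. So the documents do not support saying that pregnancy goes unchecked at crossover. They support saying that no unconditional test is required that day: Table 7 applies when a test is requested, and a criteria review does not by itself call for a test.

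**Conclusion.** The point holds as two separate wording faults that bear on patient safety. Table 4 contradicts three tests required elsewhere and drops 13 more, in tension with Section 7.5.6.1, for a woman who is under 50, not surgically sterile, amenorrheic for over 1 year and without postmenopausal FSH. Table 6, read literally, leaves exclusion 15 without a required test on the day ruxolitinib may be dispensed. The last scheduled test is then 18 to 38 days old for a Week 56 crossover within the visit windows, longer if the eligibility delay is additional, and up to about 12 weeks old for a later crossover.

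The size is small. In a trial of about 120 subjects of both sexes few women will meet all four conditions, and the documents give no basis for a number. The conclusion rests on reading the Table 4 and Table 6 notes as written, and on taking childbearing potential in Table 7 to mean what criterion 8 says, since Table 7 does not define it. The primary endpoint and its analysis are not affected.

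**What to change.** 1. In both Table 4 rows, change the note to: *Not needed if amenorrheic > 1 year and FSH in postmenopausal range*. This matches Section 7.5.6.1, whose waiver is sound and should stay.
2. Add the same route (amenorrhea over 1 year with postmenopausal FSH, at any age) to criterion 8a, so that a woman under 50 with both conditions is classed the same way throughout. She would then also fall outside the contraception condition in 8b, so this should be a deliberate choice.
3. In Table 6, delete the first mention of local regulations, so that the urine test at the eligibility visit is unconditional for women of childbearing potential.

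**Cost.** For the woman in the practical case, up to 13 more urine tests through Week 52 beyond the 3 already required elsewhere, and then the 12-weekly ones. At crossover, one urine test per woman of childbearing potential where local rules do not already require it. The Table 6 note governs the whole row, so the deletion also makes the later crossover urine tests unconditional: 13 over Weeks 4 to 52 after crossover, then one every 12 weeks. If only the eligibility test is intended, the note should say so. All are test types and visits already in the schedule. The text changes need sponsor and IRB/IEC approval (Section 10.5) and could go into the next amendment.
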